7. GENERAL OBJECTIVE

To determine the effect of the use of a nutritional support system on complications in patients with COVID-19 and comorbidities (type 2 DM, HAS, overweight/obesity with BMI <35) in stage III, compared with conventional nutritional treatment.

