2. To evaluate the effect of NSS on clinical and biochemical changes among patients.
3. To evaluate the effect of NSS on the biochemical status associated with overall mortality.

Study hypotheses

The null hypothesis: The nutritional support system will not reduce mortality or increase survival in patients with COVID-19 in stage III and comorbidities compared to conventional nutritional therapy.

Research hypothesis: The nutritional support system will reduce mortality and increase survival in patients with COVID-19 in stage III and comorbidities compared to conventional nutritional treatment.

Section 3: Trial Methods

9. Trial design - description of trial design

Item 9: Brief description of trial design including type of trial

Randomized, blinded, controlled clinical trial. Selected patients will be randomized into two groups: 1) Control Group (CG) will receive the hospital diet and 2) Intervention Group (IG) will receive the hospital diet and the NSS. Treatment allocation will have a 1:1 ratio.

10. Randomization

Randomization will be performed using a raffle; eighty numbers are to be placed (from 1 to 80). Subsequently, each number will be randomly selected from the raffle and sequentially assigned to one of the two groups, until reaching 40 numbers per group. Each number represents the moment the patient enrolls. In this way, once the recruitment starts, the first patient will be assigned number one; the second will be number two, and so on.

11. Sample size

Item 11: Full details of the same size calculation or alternatively reference to sample size calculation in protocol (instead of replication in SAP).

The sample size will be calculated using the formula: $n = \frac{z^2 p q}{e^2}$, where: 95% confidence level ($z = 1.96$), $p = 0.975$, $q = 0.025$, with a margin of error of 5% ($e = 0.05$), obtaining 38 patients per group for the sample.

12. Framework

Item 12: Superiority, equivalence or non-inferiority trial hypothesis testing framework, and wick comparisons will be presented on this basis.

The effect of NSS in increasing survival and reducing mortality in patients with COVID-19 will be demonstrated by the significant superiority of IG over CG.

13. Statistical Interim analyses and stopping guidance

Item 13a: Information on interim analyses specifying what interim analyses will be carried out and listing of time points:

No interim analyses are planned in the study.

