- SpO2 without supplemental oxygen, use of home oxygen upon hospital discharge, days of supplemental oxygen use, post-covid syndrome, decrease in body weight: all will be analyzed from hospital discharge until day 40.

Section 4: Statistical Principles

16. Confidence intervals and p-values

Item 16: Level of statistical significance

P values ≤ 0.05 will be considered indicative of statistical significance in all cases. P values will be one-sided.

Item 17: Description of any planned adjustment for multiplicity, and if so, including how the type I error is to be controlled

This study will not analyze data that required multiplicity tests. To avoid type 1 error, an alpha value of 5% will be used (considering $p < 0.05$ significant), aberrant data will be eliminated, validated tests applicable to the study variables will be defined and established, specific inclusion criteria will be implemented for homogenization of the sample to avoid bias variables, and a specific sample size calculation will be performed.

Item 18: Confidence intervals (CI) to be reported

All the confidence intervals presented will be 95%.

19. Adherence and Protocol Deviations

Item 19a: Definition of adherence to the intervention and how this is assessed including extent of exposure.

The intervention will consist of: 1) 2 envelopes of NSS taken in a period of less than 15 minutes (without the presence of vomiting) after morning and afternoon meals during the first 21 days or until hospital discharge, 2) 1 capsule of *Saccharomyces Boulardii* before the NSS and 1 capsule with the second envelope for 6 days or until hospital discharge, 3) intramuscular B complex; 1 ampoule after meals for 5 days or at hospital discharge.

Adherence to treatment will be established as taking more than 95% of the NSS and not fasting for 2 consecutive days.

Item 19b: Description of how adherence to the intervention will be presented

The intervention will be applied by the research team, who will be responsible for the application and collection of data, which will be reported in daily formats in the morning and afternoon shifts.

The clinical investigators are going to prepare each supplement, administer, and witness each intake of the NSS, registering the time as well as any immediate side effects such as vomiting, bloating, and abdominal pain.

Item 19c: Definition of protocol deviation for the trial:

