- Procalcitonin (ng / mL)

27. Analysis methods

To consider statistical significance in the results, a value of $p < 0.05$ will be used.

The analysis of the primary and secondary outcomes is shown in the following table.

Variable	Outcome	Timing	Normality test	Summary results	Parametric test	Nonparametric test	Categorical data test	Analysis type
Overall survival	Primary	40 days follow-up	-	Kaplan-Meier	-	-	Log Rank	Intergruppal
Progression to intubation	Primary	until the last patient is intubated	-	Kaplan-Meier	-	-	Log Rank	Intergruppal
Survival in intubated	Primary	40 days follow-up	-	Kaplan-Meier	-	-	Log Rank	Intergruppal
Oxygen flow (L)	Secondary	Basal vs day 3	Shapiro-Wilk	Mean and SD	Paired T test	Wilcoxon	-	Intragruppal
qSOFA (pts)	Secondary	Basal vs day 3	Shapiro-Wilk	Mean and SD	Paired T test	Wilcoxon	-	Intragruppal
Defecations per day (No.)	Secondary	Day 3	Shapiro-Wilk	Mean and SD	Unpaired T test	Mann Whitney	-	Intergruppal
Distension (Yes/No)	Secondary	Day 3	Shapiro-Wilk	Proportions	-	-	Fisher	Intergruppal
PHQ-9 (pts)	Secondary	Basal vs Discharge	Shapiro-Wilk	Mean and SD	Paired T test	Wilcoxon	-	Intragruppal
Oxygen saturation >90%	Secondary	Day 3	Shapiro-Wilk	Proportion	-	-	Fisher	Intergruppal
Hydric balance	Secondary	Day 3	Shapiro-Wilk	Mean and SD	Unpaired T test	Mann Whitney	-	Intergruppal
Bristol scale "normal"	Secondary	Day 3	Shapiro-Wilk	Proportion	-	-	Fisher	Intergruppal
Saturation without supplemental O2	Secondary	Day 40	Shapiro-Wilk	Mean and SD	Unpaired T test	Mann Whitney	-	Intergruppal
Need for supplemental O2 at home	Secondary	Day 40	Shapiro-Wilk	Proportion	-	-	Fisher	Intergruppal
Days of supplemental O2 use at home	Secondary	Day 40	Shapiro-Wilk	Mean and SD	Unpaired T test	Mann Whitney	-	Intergruppal
Postcovid syndrome	Secondary	Day 40	Shapiro-Wilk	Proportion	-	-	Fisher	Intergruppal
Decrease in weight	Secondary	Day 40	Shapiro-Wilk	Proportion	-	-	Fisher	Intergruppal
Gastrointestinal symptoms	Secondary	Day 40	Shapiro-Wilk	Proportion	-	-	Fisher	Intergruppal

28. Missing data

Item 28: Missing data-reporting and assumptions/statistical methods to handle missing data

(multiple imputation)

Statistical methods to handle missing data will not be performed.

30. Harms

Item 30: Sufficient detail provided on summarizing harms

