D dimer – ng/mL	291.2 ± 179.9	444.9 ± 954.9	0.927
Creatinine – mg/dL	0.88 ± 0.31	0.86 ± 0.22	0.734
Urea – mg/dL	33.95 ± 15.84	32.95 ± 10.78	0.710
BUN – mg/dL	15.87 ± 7.39	15.43 ± 5.02	0.690
GFR – mL/min/1.73 m ²	90.15 ± 20.2	93.59 ± 17.4	0.673
Procalcitonin – ng/mL	0.364 ± 0.6	0.18 ± 0.188	0.356

The comparison of both groups in the baseline did not show a significant difference in any item analyzed in this study.

SD, Standard Deviation. CG, control group. IG, intervention group. MNA, Mini Nutritional Assessment.

Figure 2. Kaplan-Meier general survival curve from CG and IG patients

[figure not shown]

Figure 2. Kaplan-Meier general survival curve from CG and IG patients.

The proportion of patients in the IG (blue line) and the CG (red line) included in the study and completed a 40-day follow-up from September 2020 to April 2021. The cumulative proportion of surviving patients was estimated with the Kaplan-Meier method and compared in both groups, from the CG died seven of 40 patients (surveillance 82.5%, mean 36.22, 95% of confidence interval [CI] 33.46 to 38.98), otherwise from de IG died one of 40 patients (surveillance 97.5%, mean 39.31%, 95% of [CI], 37.98 to 40.64). This showed a significant difference of IG compared to CG * $p=0.027$ (Log Rank test, 95% of [CI]).

Figure 3. Kaplan-Meier survival curve from patients Receiving Mechanical Ventilation of the CG and IG.

Figure 3-A

[figure not shown]

Figure 3-B

[figure not shown]

Figure 3. Kaplan-Meier survival curve from patients Receiving Mechanical Ventilation of the CG and IG.

The proportion of patients with MVA from CG and the IG were included in the study and completed 40-day follow-up from September 2020 to April 2021. **(Figure 3-A)** IG and CG were analyzed with the Kaplan-Meier method comparing both groups to MVA progression, from CG seven patients progressed to MVA (17.5%, mean 9.68%, [IC] of 95%, 8.66 to 9.80); meanwhile, from IG three patients progressed to MVA (7.5%, mean 9.68%, [IC] of 95%, 9.34 to 10.03), this represents a 10% decrease in MVA progression of IG in comparison with CG. **(Figure 3-B)** In overall survival and mortality with MVA, five out of seven patients died in CG (71.4%, mean 19.42, [CI] of 95%, 13.09 to 25.76). One out of three patients died in IG (33.5%, mean 26.66, [IC] of 95% 11.73 to 41.6), this represents the 38.1% decrease in mortality with MVA in IG compared to CG.

Table 2-A. Clinical evolution and 40-day follow up.

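### This version of the SAP postdates the arm-level results and the protocol does not name survival as its main outcome, so the survival claim cannot be treated as confirmatory on these documents

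*SAP*

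**What the plan says.** The SAP uses the future tense for the conduct of the trial. Item 14 has follow-up starting in September 2020, Item 13a plans no interim analyses, and Item 12 says that the effect on survival and mortality "will be demonstrated by the significant superiority of IG over CG". Item 8 makes survival and mortality the primary objective. Items 26a and 27 list three primary outcomes: overall survival to day 40, progression to mechanical ventilation, and survival in intubated patients. Item 16 states "P values ≤ 0.05 will be considered indicative of statistical significance in all cases" and "P values will be one-sided". On multiplicity, Item 17 says "This study will not analyze data that required multiplicity tests".

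The same document then reports the completed trial, September 2020 to April 2021. The Figure 2 legend says "from the CG died seven of 40 patients" against one of 40 in the intervention group, p = 0.027 by log-rank, and concludes "This showed a significant difference of IG compared to CG". The Figure 3 legend gives ventilation and deaths after ventilation by arm. Tables 1-A to 2-B are filled in with p-values.

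The protocol's general objective (section 7) is "To determine the effect of the use of a nutritional support system on complications in patients with COVID-19 and comorbidities". Mortality appears in specific objective 3 (section 7.1), with hospital stay, disease progression and progression to ventilator. Follow-up (section 8.4, Procedure) is daily for 21 days, or less if the patient is discharged or needs the ICU. The protocol has no analysis section.

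**The concern.** A nominal p-value supports a superiority claim only if the outcome, its rank and the test were fixed before anyone saw the results by arm. A plan that carries the results cannot, by itself, show this. Normally the protocol would fill the gap. Here it points elsewhere, to complications over a shorter follow-up, with no test and no ranking.

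At stake is whether 7 against 1 deaths may be presented as a demonstrated mortality benefit or only as a finding to be confirmed. With eight deaths in all, that conclusion is sensitive to choices these documents do not anchor.

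**Working it through.** **1. Reproducing p = 0.027.** Inputs are 7/40 and 1/40 deaths (Figure 2 legend). Death times are not given, so I assume distinct times and no censoring before the last death. At each death the expected number of intervention-group deaths is n1/n, with variance (n1/n)(1 − n1/n), where n1 and n are the numbers at risk in the intervention group and overall. If the single intervention death is third of the eight:

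- expected = 40/80 + 40/79 + 40/78 + 39/77 + 39/76 + 39/75 + 39/74 + 39/73 = 4.12
- variance = 1.997
- z = (1 − 4.12)/√1.997 = −2.21, giving two-sided p = 0.027 and one-sided p = 0.014

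Over all eight possible positions the two-sided value runs from 0.024 to 0.029 and the one-sided value from 0.012 to 0.014. The printed figure is therefore a two-sided log-rank value. The one-sided rule in Item 16 did not produce it.

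**2. Sensitivity to the test, same counts.**

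| Test | Two-sided p |
|---|---|
| Log-rank (printed) | 0.027 |
| Chi-square, uncorrected | 0.025 |
| Chi-square, continuity-corrected | 0.062 |
| Fisher exact | 0.057 |

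**3. The three primary outcomes of Item 26a.** The Figure 3 legend prints no p-value, so Fisher's exact test is used for the second and third.

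| Outcome | Control | Intervention | Two-sided p |
|---|---|---|---|
| Death by day 40 | 7/40 | 1/40 | 0.027 (log-rank, printed) |
| Progression to ventilation | 7/40 | 3/40 | 0.31 (Fisher) |
| Death among ventilated | 5/7 | 1/3 | 0.50 (Fisher) |

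Bonferroni over three: 0.027 × 3 = 0.081.

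**4. What free choice of the leading outcome could do.** For k independent outcomes with no true effect, the chance that the best reaches a level a is 1 − (1 − a)^k. A claim of benefit counts one direction only, so a = 0.027/2 = 0.0135. If either direction counts, a = 0.027. I take k = 3 from Item 26a and k = 5 from the protocol (complications, stay, progression, ventilation, mortality).

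| k | Favourable direction only | Either direction |
|---|---|---|
| 1 | 1.35% | 2.7% |
| 3 | 1 − 0.9865³ = 4.0% | 1 − 0.973³ = 7.9% |
| 5 | 1 − 0.9865⁵ = 6.6% | 1 − 0.973⁵ = 12.8% |

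These outcomes overlap (ventilation and death may count as progression or complications), and positive correlation lowers every figure for k > 1.

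**5. Consistency of the outcome list.** Hydric balance (p = 0.043 in Table 2-A) and day-40 gastrointestinal symptoms are in the Item 27 table but in neither Item 15 nor Item 26a.

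**The case against.** The title pages of both documents are not in the text available, so nothing can be made of a missing date or version number. The future tense in Item 14 fits drafting before recruitment, with results added to the file later. A dated pre-data SAP naming survival as primary may well exist. Mortality and ventilation were not invented by the SAP: both are in specific objective 3, and only their rank changed. A protocol without an analysis section leaves test direction and secondary measures to the SAP, so their first appearance there is not suspicious in itself. Log-rank is a natural test for survival, and Fisher's exact test is conservative with so few events. All of this stands.

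The trial's own rule also helps it. At a one-sided 5% level, one-sided Fisher is 0.028, and the one-sided log-rank value of about 0.0135 is below 0.05/3 = 0.0167, though not below 0.025/3 = 0.0083. Item 8, read alone, makes survival the only primary objective, so the factor of three would not apply; Items 26a and 27 say otherwise. These replies work only if the rules they rely on were fixed beforehand, which is the open question.

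Three stronger readings are tempting and not supported:

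- That the rules were chosen after seeing the data. The 14 secondary rows of Item 27 match Table 2-A in content and order, but a results table built from a plan would match too.
- That one-sided testing made Figure 2 significant. The printed value is two-sided and already below 0.05.
- That Figure 2 claims superiority in those words. That wording is in Item 12; the legend speaks of a significant difference.

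**Conclusion.** The concern holds in a limited form. This version of the SAP was completed with the arm-level outcomes in hand, and the protocol does not independently establish survival to day 40 as the confirmatory outcome. The survival superiority claim therefore cannot be treated as confirmatory on these documents. That describes what they can show; it does not find that anything was selected after the fact.

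The choices that matter are the outcome ranking, the test (0.027 against 0.057) and the absence of multiplicity control over three primary outcomes (0.081 after Bonferroni on the printed value, with the other two far from significance). Free choice among three to five outcomes would raise the chance of a favourable result this strong from 1.35% to about 4.0% to 6.6%. Those figures assume independence and that any of the outcomes could have been promoted. The log-rank check rests on the assumed pattern of death times, and the printed value falls inside its range.

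**What to change.** - Move Figures 2 and 3 and the filled Tables 1 and 2 to a separate results report. Keep this version in the change history; replacing the results with blank shells would hide when the document was completed.
- Identify the SAP version that existed before arm-level outcomes were seen. Mark as post hoc each outcome or rule it does not contain, including hydric balance and day-40 gastrointestinal symptoms if they are absent from it.
- Disclose the change of primary objective from complications to survival.
- Report the Figure 2 survival result as exploratory, beside the results for all three primary outcomes, unless a pre-data version names survival as primary.

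No new data are needed. The work is in the documents and in finding the earlier version. If none is found, the cost is a less favourable claim for survival.

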Categorical data will be summarized by numbers and percentages. Normality tests will be applied to evaluate the distribution of the data. If the continuous data present a normal distribution, they will be assumed by mean, SD, and range. If they do not present a normal distribution, they will be summarized with the median and the IQR. Minimum and maximum values will also be presented for continuous data. Statistical significance tests will be performed between both groups in the baseline to rule out significant differences.

Section 6: Analysis

26. Outcomes definitions

Item 26a: Specification of outcomes and timings

Primary outcomes

- Overall mortality and survival will be assessed from the baseline to day 40.
- Progression to AVM will be assessed from baseline until the last patient is intubated.
- Mortality and survival in intubated patients will be assessed from baseline to day 40.

These results will be included in the results section of the manuscript.

Secondary Outcomes

Administration of supplemental oxygen flow, oxygen saturation (spO₂), qSOFA scale, and gastrointestinal function will be assessed by comparing at baseline to day 3 intragroup and intergroup. The PHQ-9 test will be assessed at baseline and at discharge between both groups.

These results will be included in the secondary outcomes section of the manuscript. Analysis of the association of baseline biochemical parameters and mortality will be considered in a table and in the secondary outcomes section of the manuscript.

The spO₂ without supplemental oxygen requirement, home supplemental oxygen requirement, post COVID syndrome, and body weight at day 40 will be analyzed between both groups in a table.

These results are included in the follow-up section of the manuscript.

Item 26b: Specific measurement and units

- SpO₂ (%)
- Mortality (days of death)
- Kilocalories (kcal / day)
- PHQ9 (pts).
- Temperature (°C).
- Hemoglobin (g / dL).
- Mean corpuscular volume (fL).
- Mean corpuscular hemoglobin concentration (g / dL).
- Leukocytes ($10^3 / \mu\text{L}$).
- Neutrophils (%).
- Platelets ($10^3 / \mu\text{L}$).
- Glucose (mg / dL).
- Total cholesterol (mg / dL).
- Triglycerides (mg / dL).
- Aspartate aminotransferase (U / L).
- Alanine aminotransferase (U / L).
- Albumin (g/dL).
- Blood Urea Nitrogen (mg / dL).
- Urea (mg / dL).
- Creatinine (mg / dL).
- Glomerular filtration rate
- Ferritin (ng / mL)
- Fibrinogen (mg / dL)
- C-reactive protein (mg / L)
- Dimer-D (ng / mL)

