Risk factors and coexisting conditions – (%)			
Overweight	38 (95%)	36 (90%)	0.338
Obesity	14 (35%)	13 (32.5%)	1
DM 2	13 ± 0.325	11 ± 0.275	0.404
Cardiovascular disease	17 (42.5%)	10 (25%)	0.078
Hyperlipidemia	11 (27.5%)	7 (17.5%)	0.422
Gastrointestinal Disease	14 (35%)	13 (32.5%)	1
Total Risk Factors	2.92 ± 1.42	2.57 ± 1.35	0.261
Covid-19 Symptoms			
Dyspnea	24 (60%)	26 (65%)	0.409
Nausea and vomit	6 (15%)	7 (17.5%)	0.5
Hyposmia	12 (30%)	15 (37.5%)	0.637
Dysgeusia	18 (45%)	20 (50%)	0.412
Headache	26 (65%)	29 (72.5%)	0.315
Myalgia	32 (80%)	30 (75%)	0.395
Diarrhea	18 (45%)	12 (30%)	0.124
Anorexia	20 (50%)	21 (52.5%)	0.500
Total of symptoms	7.05 ± 2.11	6.8 ± 2.23	0.608
Gastrointestinal Clinic			
Bristol	9 (50%)	5 (27.8%)	0.153
Number of defecations	0.54 ± 0.6	0.52 ± 0.73	0.717
Abdominal distension	28 (70%)	28 (70%)	0.596
Vital Signs			
Breathing Frequency - bpm	21.18 ± 3.01	21.48 ± 3.01	0.378
Oxygen Saturation - %	92.73 ± 4.17	94 ± 3.18	0.144
Heart Rate - bpm	70.7 ± 15.4	75.5 ± 9.88	0.105
Temperature – °C	36.27 ± 0.73	36.3 ± 0.62	0.935
Oxygen flow – L/min	5.9 ± 3.82	6 ± 3.29	0.571
qSOFA - pts	0.425 ± 0.59	0.65 ± 0.62	0.100

SD, Standard Deviation. CG, control group. IG, intervention group.

Table 1-B. Clinical characteristics and baseline parameters of CG and IG.

Characteristics	CG	IG	P - value
	Mean (SD / %) n = 40	Mean (SD / %) n = 40	
Nutritional Status			
MNA® - pts	11.13 ± 2.26	11.38 ± 1.65	0.828
BMI – kg/m ²	29.35 ± 3.89	29.98 ± 4.07	0.403
Hydric balance – mL/day	-203.4 ± 966	-301.5 ± 1167	0.806
Medication			
Antihypertensive	13 (32.5%)	9 (22.5%)	0.227
Antidiabetics	9 (22.5%)	11 (27.5%)	0.398
Antilipids	3 (7.5%)	3 (7.50%)	0.662
Antibiotics	1 (2.50%)	4 (10%)	0.359
Antiacids	6 (15%)	6 (15%)	0.662
NSAIDs	8 (20%)	12 (30%)	0.220
Laboratory studies			
Hb – g/dL	15.53 ± 2.222	15.54 ± 2.088	0.987
MCHC – g/dL	33.39 ± 1.4	33.46 ± 1.17	0.753
Platelets – 10 ³ /μL	222.2 ± 53.93	248.4 ± 139.9	0.790
Leukocytes - 10 ³ /μL	8.97 ± 4.15	8.46 ± 4.36	0.400
Neutrophils - %	83.5 ± 8.87	80.78 ± 9.29	0.172
Glycemia – mg/dL	135.4 ± 59.39	134.8 ± 58.83	0.872
Total cholesterol – mg/dL	142.8 ± 42.82	135 ± 23.53	0.335
Triglycerides – mg/dL	147.5 ± 58.92	132.8 ± 37.39	0.533
AST – U/L	48.06 ± 28.81	46.4 ± 49.65	0.214
ALT – U/L	47.69 ± 31.9	50.44 ± 50.88	0.914
Albumin – g/dL	3.53 ± 0.44	3.57 ± 0.41	0.768
Ferritin – ng/mL	1070 ± 899.3	1270 ± 1142	0.572
Fibrinogen – mg/dL	592.2 ± 170.4	607.4 ± 162.9	0.721
CRP – mg/dL	157.3 ± 106.7	135.3 ± 94.92	0.313

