Clinical Evolution	CG				IG				Intergroup p-value
	n	Baseline	Day 3	P value	n	Baseline	Day 3	P value	
Oxygen flow - L (intragroup)	40	5.9 ± 3.8	6 ± 4.4	0.919	40	6 ± 3.2	4.5 ± 3.5	0.014 *	
qSOFA - pts	40	0.42 ± 0.59	0.51 ± 0.57	0.608	40	0.65 ± 0.62	0.43 ± 0.49	0.040 *	
Number of defecations on day 3	37		0.81 ± 0.90		36		1.41 ± 1.13		0.014 *
Distension on day 3	31		51.60%		31		19.40%		0.008 *
PHO-9 test – pts (intragroup)	6	3.66 ± 2.5	1.50 ± 2.8	0.187	10	5.3 ± 3.4	1.9 ± 1.4	0.003 *	
Oxygen Saturation >90% on day 3 -%	40		85%		40		92.50%		0.241
Hydric Balance on day 3 - mL	17		123.4 ± 453.8		18		456.6 ± 485.5		0.043 *
Bristol scale on day 3 - %	24		33.30%		31		41.90%		0.356
40-day follow-up			Day 40				Day 40		
Saturation without Supplementary Oxygen - %	28		90.39 ± 3.4		38		92.08 ± 2.5		0.030 *
Need for home Oxygen flow - %	27		85.2%		39		66.70%		0.078
Time of home Oxygen use – days	17		57.6 ± 24.6		23		43.8 ± 16.2		0.098
Post-covid syndrome - %	24		37.50%		34		23.50%		0.195
Weight decrease - % of patients	11		72.70%		18		44.40%		0.135
Gastrointestinal symptoms - %	24		16.70%		37		8.10%		0.266

Table 2-A The following table shows the results of the intergroup analysis between the IG (Intervention Group) and the CG (Control Group) for different parameters in the baseline or with a complete 40-day follow-up. Deceased patients were excluded. * p-value <0.05.

Table 2-B. Association of baseline laboratory parameters and general mortality.

Baseline values	Discharge (n=72)		Death (n=8)		P value
	n	%	n	%	
Fibrinogen >700 mg/dL	13	18.50	6	75.00	0.002 *
Procalcitonin >0.5 ng/mL	4	5.5	4	50	0.003 *
Blood Urea Nitrogen >22 mg/dL	5	6.90	4	50	0.004 *
RCP >150 mg/L	28	38.8	7	87.5	0.011 *
Neutrophils >80%	45	62.50	8	100	0.031 *
Leucocytes >10 10 ³ /μL	18	25.00	5	62.50	0.040 *
Urea >40 mg/dL	12	16.6	4	50	0.047 *

Table 2-B. The results show the association between laboratory parameters taken in the baseline, with the overall mortality. Analysis was performed with Fisher's exact test. * p-value < 0.05.

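### Table 2-B relates death to seven baseline markers at cut-offs the SAP never sets and counts urea twice, so it supports neither a count of seven nor those cut-offs.

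*SAP*

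**What the plan says.** SAP Item 26a, under secondary outcomes, states: "Analysis of the association of baseline biochemical parameters and mortality will be considered in a table". It names no markers, thresholds or test. Item 26b lists 21 laboratory parameters with their units only, apart from GFR, which has none; no thresholds are given. Item 27 introduces its methods table with "The analysis of the primary and secondary outcomes is shown in the following table", but that table has no row for this analysis.

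On error control, Item 16 says "P values will be one-sided" and sets the level at 0.05. Item 17 says "This study will not analyze data that required multiplicity tests" and plans no adjustment.

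Table 2-B, already filled with results, compares 72 discharged patients with 8 who died, on seven dichotomised markers: fibrinogen, procalcitonin, BUN (the row reads "Blood Urea Nitrogen >22 mg/dL"), CRP, neutrophils, leukocytes and urea. Every row is starred. The test is named only in the legend: "Analysis was performed with Fisher's exact test". Table 1-B, the baseline comparison of the arms, has 20 laboratory rows, which are the Item 26b list without mean corpuscular volume.

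**The concern.** Item 26a limits the analysis to no subset, yet 13 of the 20 Table 1-B laboratory items (14 of the 21 in Item 26b) have no row in Table 2-B. Every row that is shown is significant. By contrast, Table 2-A prints its non-significant rows. A reader of Table 2-B cannot tell whether the other markers were tested, or when and why each threshold was chosen.

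With 8 deaths, a dichotomised comparison turns on very few patients, so the choice of threshold can move a p-value a long way. Listing BUN and urea separately also makes one measurement look like two findings that agree. What is at stake is the credibility of the marker list and its cut-offs. The table pools both arms, so no treatment comparison or primary outcome depends on it.

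**Working it through.** **1. Reproducing the printed p-values.** For each row, Fisher's exact test on the 2x2 table of marker above or below the cut-off by death (n=8) or discharge (n=72), using the counts in Table 2-B:

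| Marker and cut-off | Discharged | Died | Printed p | One-sided | Two-sided |
|---|---|---|---|---|---|
| Fibrinogen >700 | 13 | 6 | 0.002 | 0.0018 | 0.0018 |
| Procalcitonin >0.5 | 4 | 4 | 0.003 | 0.0026 | 0.0026 |
| BUN >22 | 5 | 4 | 0.004 | 0.0045 | 0.0045 |
| CRP >150 | 28 | 7 | 0.011 | 0.0113 | 0.0187 |
| Neutrophils >80% | 45 | 8 | 0.031 | 0.0306 | 0.0463 |
| Leukocytes >10 | 18 | 5 | 0.040 | 0.0400 | 0.0400 |
| Urea >40 | 12 | 4 | 0.047 | 0.0468 | 0.0468 |

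All seven match the one-sided values (BUN is 0.00448 before rounding), in line with Item 16. All seven also stay below 0.05 two-sided.

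**2. BUN and urea are one analyte.** Urea divided by BUN, from Table 1-B:
- Control means: 33.95/15.87 = 2.139; intervention means: 32.95/15.43 = 2.135.
- Control SDs: 15.84/7.39 = 2.143; intervention SDs: 10.78/5.02 = 2.147.

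Means and SDs that scale by the same constant in both arms are what one quantity in two units looks like. Converting the cut-offs: 22 x 2.139 = 47.1 mg/dL of urea, and 40/2.139 = 18.7 mg/dL of BUN. The thresholds differ by about 18% (47.1/40 = 1.18). Lowering the urea-scale threshold from about 47 to 40 raises the number flagged from 9 (5+4) to 16 (12+4). That adds seven survivors and no deaths, and moves p from 0.0045 to 0.0468, about tenfold. Counting urea once leaves 7 - 1 = 6 distinct markers.

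**3. Multiplicity, assuming all listed markers were tested.** Undisplayed p-values are set to 1; m = 20 (Table 1-B) or 21 (Item 26b).
- Bonferroni: 0.05/20 = 0.0025 and 0.05/21 = 0.0024. One row survives either way (fibrinogen).
- Holm, m = 20: the second step needs p at or below 0.05/19 = 0.00263. Procalcitonin passes with its exact p of 0.00260 and fails with the printed 0.003, so two rows or one. Holm, m = 21: one row.
- Benjamini-Hochberg: three rows (fibrinogen, procalcitonin, BUN), with adjusted p of about 0.03. CRP is next at 20 x 0.0113/4 = 0.056 and fails.

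**4. How far chance could go.** With 20 independent tests at 0.05, one false positive is expected and the chance of at least one is 1 - 0.95^20 = 0.64. The chance of seven or more is about 0.00003, under independence and fixed cut-offs. As an illustration of threshold risk only: for a simulated null marker with 8 deaths among 80, one-sided Fisher gives 2.8% false positives at a fixed median cut and 13.7% at the best of nine decile cuts. Over 20 markers that is 0.56 against 2.7 expected false hits.

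**5. The fibrinogen percentage.** 13/72 = 18.06%, but the table prints 18.50%; 13/70 = 18.57%. Other rows appear to be cut rather than rounded (12/72 = 16.67%, printed 16.6), so two missing survivors would fit, though a misprint is also possible. With 70 survivors p is 0.0021, still printed as 0.002.

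**The case against.** A reader might infer that exactly seven of 20 markers reached p<0.05 and the other 13 were tested and hidden. The documents do not show this. Table 1-B compares the arms at baseline and is not a list of mortality tests, and nothing says that the remaining markers were dichotomised or tested. Selective display is a reasonable suspicion, not a documented fact.

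A reader might also infer that each threshold was searched for. No evidence supports that, and the urea rows point the other way: an analyst looking for the best cut would have used the equivalent of BUN 22, which gives 0.0045, and not urea 40, which gives 0.0468. All the cut-offs are round numbers and may have an outside source.

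Nor can the table be dismissed as chance. Seven hits exceed the roughly 2.7 of the worst-case illustration; at 13.7% per marker, seven or more of 20 has probability about 0.014 under independence, although correlation between markers weakens that figure. Finally, the title and legend claim association only, not independent prediction or usable cut-offs.

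These objections remove the stronger readings. They leave standing the absent specification, the double-counted analyte, the lack of multiplicity control and the unreported markers.

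**Conclusion.** The point holds in a limited form. The SAP gives no marker subset, cut-off or test for this analysis before Table 2-B, and the seven starred rows represent at most six analytes. If all 20 or 21 listed markers were tested, one to three rows survive adjustment; that range rests on an assumption the documents neither confirm nor rule out. Some association between baseline laboratory values and death is probably real. What the table does not support is the count of seven and the specific thresholds. The fibrinogen percentage is a reporting correction and does not change its p-value. The matter should be corrected, but it concerns a secondary, pooled, non-randomised comparison and does not touch the primary outcomes.

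**What to change.** - In Items 26a and 27, specify that every Item 26b laboratory value, keeping only one of BUN and urea, is analysed at baseline as a continuous variable against death, using Mann-Whitney and the AUC with its 95% confidence interval.
- Report all markers whatever their p-value, with either a multiplicity-adjusted p-value (Holm or Benjamini-Hochberg) or an explicit exploratory label.
- Label the Table 2-B cut-offs as not pre-specified and exploratory, unless a source that predates the data is cited.
- Print the denominator in each row, and correct or explain the fibrinogen percentage.

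The cost is a change of SAP wording and a re-run on data already held. The downside is a longer table with fewer starred rows.
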